**1.0 SUMMARY**

This is a prospective, non-randomized, longitudinal study of the clinical outcomes of participants that receive the Stryker Triathlon® Total Knee System for Total Knee Arthroplasty implanted using ShapeMatch® Cutting Guides. Health status and functional outcome measures will be recorded to quantify functional status of subjects before surgery and at each follow-up interval.

There will be 4 sites and 6 investigators for this study. A maximum of 160 cases will be enrolled in the study and it is expected that participants will be recruited over a 6 month period. Total duration of the study is expected to be 1.5 years.

The study consists of two groups:

Group A: Assessment of the intra-operative reproducibility of placement of the ShapeMatch® Cutting Guides onto the distal femur and proximal tibia bone surfaces;

Group B: Assessment of the placement of the ShapeMatch® Cutting Guides intra-operatively combined with an assessment of post-operative patient outcomes compared to pre-operative status and post-operative implant placement.

Pre-operatively, all participants will be required to undergo medical imaging assessment using Magnetic Resonance Imaging (MRI) of the affected lower limb. These images will then be used to manufacture the patient-specific cutting guides for preparation of the bones prior to implantation of the total knee replacement.

For Group A, participants will only undergo intra-operative assessments to determine repeatability of the placement of the cutting guides onto the distal femur and proximal tibia. No post-operative evaluations will be specifically required of participants due to their involvement in this study.

For Group B, participants will be requested to attend visits pre-operatively and post-operatively at 6 weeks, 3 months and 6 months. At these visits will complete assessments relating to quality of life, pain and functional outcome. In addition, participants will have standard knee X-rays taken pre-operatively and post-

operatively. A post-operative CT scan will be obtained for all participants in order to assess implant position and orientation.

All implanted prosthetic components (Stryker Triathlon Primary Total Knee System) used in this study are TGA approved for sale and use in Australia. This study was originally to be undertaken via the Clinical Trial Notification (CTN) Scheme of the Therapeutic Goods Administration (Therapeutic Goods Act, 1989); however the ShapeMatch® Cutting Guides are now also listed on the Australian Register of Therapeutic Goods (ARTG) for sale and use in Australia.

This study will adhere to all relevant requirement and guidelines in relation to the conduct of clinical trials, including the Declaration of Helsinki (Appendix 5) and ICH Good Clinical Practice Guidelines, as implemented in Australia (Appendix 6).

An Extension Study will be undertaken to follow Group B patients who consent to continued follow-up. These patients will be followed out to 5 years post-surgery with follow-up visits at 12 months, 2 years and 5 years in order to collect longer term data on radiographic and patient outcomes.

### **Visit Windows**

Definition – Since it is not always possible for subjects to come in for a study visit on the exact date, most protocols allow a certain time period before or after the calendar date; this is known as the visit window. If a subject is not seen during the visit window, that visit will be regarded as a missed visit. Visit windows are calculated in reference to the baseline date, which is the surgery date (intra-op) for this study.

### Patient Evaluation Schedule

#### Part A: Reproducibility sub-study

EVALUATION	History/ Pre-Op	Intra-Op
Demographics	✓	
Medical History	✓	
MRI	✓	
Surgical Details		✓

Note: No post-op visits required for participants in Part A.

The visit windows for this study are:

- Pre-Op = Within 2 months before the date of surgery

#### Part B: Functional outcome sub-study

EVALUATION	History/ Pre-Op	Intra-Op	6 week	3 MO	6MO
Demographics	✓				
Medical History	✓				
MRI	✓				
Surgical Details		✓			
International Knee Society Score	✓			✓	✓
KOOS	✓		✓	✓	✓
SF-12 v2	✓		✓	✓	✓
VAS Pain	✓		✓	✓	✓
AP and ML X-rays	✓		✓		
Perth CT Protocol				✓	✓*

The visit windows for this study are:

- Pre-Op = Within 2 months before the date of surgery
- Intra-op = Baseline time point
- 6 Weeks = +/- 2 weeks
- 3 Months = +/- 1 month (+/- 6 weeks for CT only – except WA site)
- 6 Months = +/- 1 month(+/- 6 weeks for \*CT WA site Only and X-ray only)

Extension Phase:

EVALUATION	12 month follow-up	2 year follow-up	5 year follow-up
Demographics	✓		
BMI	✓	✓	✓
Medical History Review	✓		
Surgical Details	✓		
Knee Society Score	✓	✓	✓
KOOS	✓	✓	✓
SF-12 v 2	✓	✓	✓
VAS Pain	✓	✓	✓
Forgotten Joint Score	✓	✓	✓
Anteroposterior (A/P) and Lateral Knee Radiographs	✓		✓
Long leg (A/P) weight bearing x-ray	✓		✓
Adverse Events	✓	✓	✓

The visit windows for this study are:

- 12 Months = +/- 3 months
- 2 years = +/- 3 months
- 5 years = +/- 4 months

## 2.0 INTRODUCTION

Total knee replacement has evolved to a point where implant design combined with instrumentation and surgeon skill results in excellent implant survival. Over 30,000 total knee replacement procedures are performed each year in Australia and are used to treat a range of conditions including osteoarthritis, rheumatoid arthritis, avascular necrosis and secondary arthritis resulting from trauma.

Current surgical techniques make use of generic, re-usable instrumentation, consisting of intra- and/or extra-medullary rods on the femur and tibia to determine alignment in relation to anatomical landmarks, combined with bone resection guides which ultimately determine position and orientation of the definitive implant components.

[figure not shown]
Traditionally, the goal of total knee replacement has been to position the components such that the post-operative alignment goal is a straight limb, or a mechanical axis of 0° (Insall & Scott, 2001). The mechanical axis is defined by lines joining the centre of the femoral head, centre of the knee joint and the centre of the ankle. Despite the best efforts of the surgeon, the resulting limb alignment varies away from 0° by a small amount (typically  $\pm 3^\circ$  in 80% of cases).

More recently, the use of computer navigation systems has been introduced to surgical practice with the aim of improving the ability to obtain post-operative limb alignment as close as possible to 0° (Chauhan et al, 2004).

[figure not shown]
Whilst achievement of neutral limb alignment has been considered desirable from an engineering point-of-view – to maximize implant longevity through minimizing the deleterious effects of polyethylene insert wear and particle-induced osteolysis and implant loosening – patient satisfaction of total knee replacement has not always been ideal. Despite surgery being performed technically correct by surgeons, up to 1 in 5 patients express dissatisfaction in the functional result (Bourne et al, 2009). Patient expectations after surgery are also increasing due in part to the adoption of more active lifestyles amongst total knee replacement recipients where return to function can be of primary importance.

The opportunity exists to provide an alternative approach to total knee replacement surgery which may result in improved patient outcomes. One such approach is to determine the optimal placement of components based on the individual anatomy of patients, rather than a generic limb alignment philosophy (Coughlin et al, 2003; Eckhoff et al, 2005). This approach relies on the creation of a pre-arthritis model of the bone and cartilage structures of the knee. A single, 3-D axis of rotation is then determined which takes into account the 3-D shape and orientation of the femoral condyles during the weight-bearing portion of gait. This is in contrast to traditional surgical techniques which set femoral component orientation and position using one or more of the trans-epicondylar axis, posterior-condylar axis and/or the anterior-posterior (or Whiteside's) line. This new axis is then the basis of determining the so-called natural alignment goal for the joint replacement procedure.

A comprehensive three-dimensional description of the anatomy can be obtained by magnetic resonance imaging (MRI) scans obtained pre-operatively. Through a proprietary process, it is possible to pre-operatively develop a model of the arthritic bone and cartilage, adapt that model to take into account degenerative process, and generate a model of the pre-arthritis anatomy (Appendix 1, Fig. 1). The pre-arthritis state then becomes the surgical goal in terms of limb alignment. Custom cutting guides are generated for each individual patient to enable the surgeon to perform the bone resections in such a way that the resultant construct with the total knee replacement components reproduces the pre-disease limb alignment (Fig. 2). Early experience of applying this technique indicates that patient outcomes and function assessed during the early post-operative phase are superior to conventional approaches to total knee replacement (Howell et al, 2008; Spencer et al, 2009). Other potential advantages of this technology include a reduction in blood loss (as no intramedullary rod is used), and a reduction in ligament releases (as the total knee components effectively resurface the knee with restoration of the natural alignment) (Howell et al, 2008).

**Figure 1:** Workflow and data transfer process used for preparation of ShapeMatch® Cutting Guides.

**Figure 2:** Intra-operative image of ShapeMatch® Cutting Guides positioned on distal femur and proximal tibia. Femoral cutting guide has been pinned in place, ready for bone resection. Tibial cutting guide being positioned prior to pinning.

This protocol outlines a study for the systematic assessment of this new approach to total knee replacement.

This study consists of two distinct parts:

Group A: This sub-study aims to quantify the reproducibility of positioning the cutting guides onto the affected femoral and tibial joint surfaces.

Group B: This sub-study aims to assess certain aspects of the operative procedure, as well as measure parameters relating to quality of life, pain and functional outcome using standard orthopaedic scoring methods.

Following on from Group B, an extension study will be undertaken. This study aims to determine the clinical and radiographic outcomes out to 5 years post surgery, in patients receiving a Triathlon Custom Fit Knee featuring Stryker ShapeMatch

### **3.0 OBJECTIVES**

The primary endpoints of this study are:

1. Repeatability of cutting guide position on the distal femur and proximal tibia assessed by repeated measures using computer navigation system for total knee replacement, assessed intra-operatively (Group A).
2. Radiographic implant location, consisting of multi-parameter assessment of the relative position and orientation of the femoral and tibial components and overall limb alignment, assessed by the Perth CT protocol 3 months after surgery (Group B).

The secondary endpoint of this study is:

3. Knee function, quality of life and pain assessed 6 months after surgery (Group B).

The study objectives are:

1. Repeatability of the cutting guide position will be no worse than that obtained for manual instruments used for total knee replacement (Group A).

2. Participants will have higher knee function scores and increased quality of life as compared to pre-operative state and equal or better as compared to other surgical techniques using historical controls (Group B)

The objectives of the Extension Study are:

1. The primary objective is to determine the clinical and radiographic outcomes at 12 months, 2 years and 5 years post surgery, in patients receiving a Triathlon Custom Fit Knee featuring Stryker ShapeMatch.
2. The secondary objective is to determine the revision rate (yearly cumulative percent revision), device-related adverse events and reoperation rates.

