## RESEARCH OBJECTIVES

The use of patient-specific cutting guides for total knee joint replacement is being developed and introduced to clinical practice by a number of orthopaedic device companies. Each system differs in the way in which the cutting guides are designed, the material which they are made from, the alignment philosophy and the radiological information on which they are based (e.g. X-ray, CT, MRI).

The overall goal of this study is to assess the impact of a new surgical technique developed by Stryker on the functional outcome of participants undergoing primary total knee joint replacement.

The repeatability in placing the cutting guides relies on the reference points used in the design of the block, and the ability of the surgeon to position it on the diseased joint surfaces of the knee without the availability of traditional alignment jigs (femoral intra-medullary rod, tibial extra- or intra-medullary alignment guide). Hence, the first objective of this study is to quantify the reproducibility of this new technique by assessing cutting guide position using a repeated-measures methodology. The results will be described as a standard error of measurement.

Early reports indicate that improved post-operative functional outcomes may result from the use of this new technology when used in combination with particular designs of total knee joint prosthetic components (Howell et al, 2008; Spencer et al, 2009). The second objective is to assess and quantify such changes in the short-term (6

months) post-operative period. Potential benefits may be seen in the general quality of life experienced by participants, reduced pain levels, and specific improvements in activities of daily living affected by knee function. Other parameters related to the procedure, such as operating time, blood loss and length of stay in hospital will also be assessed to determine if perceived benefits with the use of this new surgical technique can be realised in routine clinical practice. Comparison of the study findings will be made to published literature on the clinical outcomes of total knee replacement (e.g. Kolisek et al, 2007; Matziolis et al, 2007; Harwin et al, 2008).

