**7.0 STUDY DESIGN**

**Group A:** This is a repeatability study of ShapeMatch® patient-specific cutting guides designed for participants undergoing total knee arthroplasty with the Triathlon® Total

Knee System (Stryker Orthopaedics, Mahwah NJ, USA) and Stryker eNact Knee Navigation System (Stryker Navigation, Kalamazoo MI, USA). Participants will undergo pre-operative assessment using MRI of the affected limb according to the scan protocol (see Appendix 2 for example). At the time of surgery, a repeated-measures methodology will be implemented in which the position of the femoral and tibial cutting guides will be measured using the Navigation system. The same surgeon will position each cutting guide a total of 3 times for each patient. Multiple participants will be assessed by each surgeon. No bone resections will take place using the patient-specific cutting guides. After the study-specific measurements have been taken, the total knee procedure will resume using the Navigation system and associated instruments being used to prepare the distal femur and tibia prior to implantation of the Triathlon® total knee components. No post-operative evaluations will be undertaken as part of this sub-study. However, participants will have routine visits, as per the investigators' standard-of-care for such participants.

Approximately 30 participants (5 per investigator) up to a maximum of 60 participants will contribute to this sub-study.

**Group B:** This is a consecutive sample survey of participants undergoing total knee arthroplasty with the Triathlon® Total Knee System (Stryker Orthopaedics, Mahwah, NJ USA) utilizing ShapeMatch® patient-specific cutting guides to prepare the bony resections on the distal femur and proximal tibia. Health status and functional outcome measures will be recorded to quantify functional status of subjects before surgery and at each follow-up interval.

Participants suitable for primary total knee arthroplasty and indicated for computer-assisted surgery will be booked for surgery. Recruitment will be subject to gaining suitable informed consent from the patient.

Participants will undergo pre-operative assessment using MRI of the affected limb according to the scan protocol (Appendix 2).

Appropriate total knee replacement components from the Stryker Triathlon® Total Knee System will be used.

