## **9.0 SURGICAL PROCEDURES**

### **Group A:**

Each patient will be prepared to undergo a primary total knee replacement using the Triathlon Primary Total Knee System and Stryker eNact Knee Navigation System. A standard skin incision and joint exposure will be performed according to the surgeon's

preference. Navigation trackers will be secured to the femur and tibia and registration of the limb will be undertaken according to the surgical technique.

The appropriate Stryker ShapeMatch® Cutting Guide will be positioned onto the distal femur. A Navigation tracker with Resection Plane Probe attached will be placed into the cutting slot of the cutting guide. The location (position and orientation) of the probe is displayed on the computer screen of the Navigation system. The screen will be diverted from the surgeon's view and a recording will be made of the position once the surgeon has indicated that the cutting guide is positioned appropriately. The cutting guide will then be removed from the femur, and the process repeated until a total of three measurements have been recorded. The same procedure will be performed on the proximal tibia using the appropriate Stryker ShapeMatch® Cutting Guide. This entire process should take no longer than 5 minutes.

Once these measurements have been performed, the surgeon will resume the surgical technique for implantation of the Stryker Triathlon Primary Total Knee System using Stryker eNact Knee Navigation System, as per their own instrument and implant preferences.

Appropriate post-operative care will be provided according to the preference of the treating physician. No further evaluations will be required by study participants.

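### Objective 1 claims guide repeatability no worse than manual instruments, but Group A measures only the custom guides and the plan sets no manual value, margin or rule

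*Combined protocol and SAP*

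**What the plan says.** **The comparative wording.** Section 3.0 (Objectives) makes repeatability of guide position primary endpoint 1 for Group A. The matching study objective is: "Repeatability of the cutting guide position will be no worse than that obtained for manual instruments used for total knee replacement (Group A").

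**The descriptive wording.** Section 2.0 (Introduction) gives Group A's aim as: "This sub-study aims to quantify the reproducibility of positioning the cutting guides onto the affected femoral and tibial joint surfaces". The Research Objectives text under Section 3.0 says that "the first objective of this study is to quantify the reproducibility of this new technique by assessing cutting guide position", and then: "The results will be described as a standard error of measurement". Neither mentions manual instruments as a comparator.

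**What is measured.** Section 7.0: "The same surgeon will position each cutting guide a total of 3 times for each patient". Section 9.0 describes the same cycle, with "the process repeated until a total of three measurements have been recorded", first on the femur and then on the tibia. After that, "the total knee procedure will resume using the Navigation system and associated instruments being used to prepare the distal femur and tibia".

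**What is analysed.** Section 12.2 plans a repeated-measures analysis giving a mean and an SEM from successive pairs of trials, pooled over surgeons. Section 12.1 states that Group A is a convenience sample without a sample size calculation. Section 7.0 expects about 30 patients, with a maximum of 60.

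**The concern.** One objective appears in two forms. The comparative form needs something to compare with: a manual-instrument SEM, a statement of how much larger the guide SEM may be and still count as no worse, and a rule linking the estimate to the conclusion. The plan supplies none of these for Group A.

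This objective goes with a primary endpoint. If the wording stays, a descriptive SEM could be reported as having met a comparative objective, with the benchmark and the meaning of no worse both chosen after the data are seen.

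**Working it through.** **1. Is there a manual comparator anywhere in the plan?** The plan states no Group A margin, power or benchmark, so there is no figure to reproduce. The candidate sources are:

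- *Group A measurements (7.0, 9.0).* Only the custom guide is repeatedly placed and recorded. The operation then continues with navigation. No manual jig placement is measured.
- *Historical controls (3.0).* These are named in objective 2, for Group B.
- *Literature comparison (Research Objectives).* "Comparison of the study findings will be made to published literature on the clinical outcomes of total knee replacement". This concerns clinical outcomes, not guide placement.
- *Tests chosen by a biostatistician (12.2).* This sentence is in the paragraph on Group B and the Extension Study, and would not define no worse in any case.
- *Limb alignment typically within 3° in 80% of cases (2.0).* This is variation between patients in post-operative alignment, not within-patient repeatability of placing a guide.
- *Cadaver study (end of Research Objectives).* This is a separate, planned study of cutting-guide placement. No manual arm is mentioned.

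None supplies a manual SEM, a margin or a rule.

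**2. What can the design estimate?** Inputs from the plan: n = 30 or 60 patients and 3 placements each. Assumptions: one parameter, independent normal errors, equal variance across surgeons and knees, and placement order fitted as a fixed effect. Then df = 2(n − 1), which is 58 or 118.

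The 95% limits, as multiples of the estimated SEM, are √(df/χ²₀.₉₇₅) and √(df/χ²₀.₀₂₅):

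| n | df | χ²₀.₀₂₅ | χ²₀.₉₇₅ | Lower | Upper |
|---|---|---|---|---|---|
| 30 | 58 | 38.84 | 80.94 | √(58/80.94) = 0.847 | √(58/38.84) = 1.222 |
| 60 | 118 | 89.83 | 149.96 | √(118/149.96) = 0.887 | √(118/89.83) = 1.146 |

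That is useful precision for a descriptive aim.

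**3. What happens if no worse is settled by eye?** Suppose the point estimate is simply set against a fixed manual SEM, with r the true guide/manual SEM ratio. The chance of passing is P(χ²_df ≤ df/r²). With n = 30:

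- r = 1.0: P(χ²₅₈ ≤ 58) = 0.52
- r = 1.1: P(χ²₅₈ ≤ 58/1.21 = 47.93) = 0.18

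Truly equal guides would pass about half the time, and guides with a 10% larger SEM would pass about one time in six.

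**4. What would a proper rule need?** Conclude no worse if the upper limit of the two-sided 95% interval for the SEM ratio is below a margin m. With a fixed benchmark and truly equal SEMs, the rule passes when χ²_df < m²·χ²₀.₀₂₅, so 80% power needs m = √(χ²₀.₈₀/χ²₀.₀₂₅):

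- n = 30: √(66.82/38.84) = 1.31
- n = 60: √(130.70/89.83) = 1.21

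The choice of limit matters. A one-sided 95% limit uses χ²₀.₀₅ (41.49 and 93.92) and gives √(66.82/41.49) = 1.27 and √(130.70/93.92) = 1.18.

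If the benchmark is itself an estimate with b df, m = √(F₀.₈₀(df, b) × F₀.₉₇₅(b, df)). Assuming b equal to the Group A df, this is 1.45 (n = 30) or 1.30 (n = 60).

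**The case against.** The strongest reply is that Group A is openly an estimation study. Endpoint 1 contains no comparator, Section 12.1 disclaims a sample size calculation, Section 23.0 calls the document a case series protocol, and the Research Objectives text presents the results as groundwork for later randomised trials. On that view the objective is a loosely worded expectation, and the planned SEM is usable whether or not the sentence changes. This stands as far as it goes: it limits the weight of the point and supports a simple rewording. It does not make the comparative sentence supportable.

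A reader might infer more than the documents support:

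- *That Group A is unsound or needs a manual control arm.* It does not follow. The descriptive aim is met by the planned measurements, and an SEM could support a comparison with an external value once that value and a margin were fixed.
- *That the sponsor intends an unsupported claim.* Nothing in the plan schedules one. The risk lies in what the wording would permit.
- *That the successive-pairs SEM or the pooling of surgeons is wrong.* Section 12.2 cites a method source that was not available here and may explain how pairs are combined. The Research Objectives text assigns intra- and inter-observer variation to the cadaver study. A single-model SEM or SEMs by surgeon would be optional additions and are not part of this point.

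**Conclusion.** The point holds as a mismatch between the wording of objective 1 and everything planned to address it. As written, the plan cannot support a conclusion that guide placement is no worse than manual instruments. This finding rests on the text alone and on none of the calculations.

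The calculations show two things under the stated assumptions. The design serves the descriptive aim well, with limits of 0.85 to 1.22 times the SEM at n = 30 and 0.89 to 1.15 at n = 60. A comparative claim would need a fairly wide margin even with a fixed benchmark, about 1.31 or 1.21 for 80% power on one parameter. Unequal variances between surgeons, an uncertain benchmark, or a requirement that several parameters all pass would make the claim harder to support. The matter should be corrected, but it is a wording reconciliation and raises no patient-safety issue.

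**What to change.** **Preferred.** In Section 3.0, replace objective 1 with: to estimate the repeatability of guide placement (SEM with 95% CI) for each position and orientation parameter. Drop the comparison with manual instruments. This brings Section 3.0 into line with the Introduction, the Research Objectives text and Section 12.1. Section 12.2 needs only the confidence interval added.

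**Only if the claim is kept, and Group A has not yet been analysed.** Fix beforehand, for each parameter, a manual-instrument SEM from a named source and a ratio margin with its justification. State whether all parameters must pass. Conclude no worse only if the upper limit of the two-sided 95% CI for the guide/manual SEM ratio, allowing for uncertainty in the source value, lies below the margin. The documents do not say whether Group A has been analysed. Its enrolment was expected to take 3 months, and this version already adds the Extension Study, so rewording may be the only route left.

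**Cost.** One reworded objective and a line in Section 12.2, submitted for ethics approval as Section 18.0 requires. No new patients or measurements are needed. The sponsor gives up a statement that the plan cannot support or, under the second route, must find a manual value and defend a margin.
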